# Secondary effectiveness analysis

The secondary endpoints as listed in Section 3.4.2 will be compared between the treatment groups for the time points recorded (Table 2). Comparisons between the treatment groups will be based on 95% confidence intervals.

Beyond the secondary endpoints in the secondary hypotheses, all stated quantitative secondary endpoints should be analyzed using repeated measures modeling. This will control for any effects expected to be significant. The response and/or explanatory variables may need to be transformed depending on their ability to meet the assumptions of the model.

Through using repeated measures modeling and the randomization scheme proposed we may disregard any specific implant within quadrant randomization and the need to limit measure comparisons between two implants alone. This maintains result integrity by including all information in the analysis. Furthermore, secondary variables that have measures across more than two time-points are analyzed with these methods with no loss in data.

The survival analysis will be carried out over the study implants (study control and study test implant) placed at the surgery visit (V2) and within the ITT population. Implant survival will be analyzed using the Kaplan-Meier Survival estimate with Confidence Intervals (CI) given by the Greenwood formula. Considering that for this study the number of patients not completing the 12 months follow-up visit may exceed 5% due to missed follow-up visits, the formula of Rothman will used for confidence intervals.

## Safety and tolerability analysis

The safety analysis will be performed on data collected as specified under 7.3.12 and 7.3.13

The analysis of safety assessments in this study will include summaries of the following of safety and tolerability data collected for each subject:

- Adverse events
- Serious adverse events
- Adverse device effects
- Device deficiencies
- Device deficiencies that could have led to a serious adverse device effect

Summaries of the incidence rates (frequencies and percentages), severity, outcome and relationship to the investigational device and or/ study procedures of individual AEs will be

prepared. AEs which concern an implant position where a BLT, Roxolid® implant was placed during surgery or AEs which are related to a treatment procedure at such a position will be summarized by study treatment and overall and the used products at this position will be listed.

DDs will be summarized per medical device type (implant type, abutment type, instruments).

To address the co-primary objective of this study "SLActive® implants are safe" a descriptive assessment of adverse device effects and device deficiencies that could have led to a serious adverse device effect will be made, this will include listings and tables by treatment, severity, relatedness and outcomes.

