# 2 Objectives

#### 2.1 Study Hypothesis

Based on previous obtained data the expectations are as follows:

Co-primary study hypotheses:

- 1) SLActive® implants are safe
- 2) 12 months after loading, the marginal bone loss around the SLActive® implants will not be appreciably greater than around the SLA® implants.

Secondary study hypotheses:

- SLActive® implants show superior osseointegration compared to SLA® as tested by biomarker analysis
- 4) SLActive® implants show superior anti-inflammation compared to SLA® as tested by biomarker analysis

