# 3.4 Endpoints

#### 3.4.1 Primary Endpoint

The following parameter will be measured as primary endpoint:

- Bone level change 12 months after implant loading.
- Occurrence of adverse device effects and device deficiencies that could have led to a serious adverse device effect

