#### 9.2 Effectiveness analysis

A detailed description of the effectiveness analysis can be found in the statistical analysis plan (SAP).

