## Safety Analysis Population (SA)

The safety analysis (SA) population consists of all subjects who were enrolled in the study and who received a study device (BLT, Roxolid® implants).

The SA population will be the basis for the safety analysis.

This population includes the ITT population.

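### Co-primary hypothesis 1, that SLActive implants are safe, is answered by counts alone, with no interval, no within-patient estimate and no criterion set in advance

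*Combined protocol and SAP*

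**What the plan says.** The Synopsis and section 2.1 list two co-primary hypotheses. The first is "SLActive® implants are safe"; the second concerns marginal bone loss. Section 3.4.1 gives the first its own primary endpoint: "Occurrence of adverse device effects and device deficiencies that could have led to a serious adverse device effect".

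The safety and tolerability part of section 9.2 states how that hypothesis is addressed: "a descriptive assessment of adverse device effects and device deficiencies that could have led to a serious adverse device effect will be made", and "this will include listings and tables by treatment, severity, relatedness and outcomes". The general adverse-event output is "Summaries of the incidence rates (frequencies and percentages), severity, outcome and relationship to the investigational device". Under section 9.3, "The SA population will be the basis for the safety analysis"; that population is everyone enrolled who received a BLT Roxolid implant.

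Elsewhere the plan is more specific. For secondary endpoints, section 9.2 says "Comparisons between the treatment groups will be based on 95% confidence intervals", and implant survival gets Kaplan-Meier estimates with intervals. Section 9.4 sets a null hypothesis, margin, one-sided alpha and power, all for bone loss. Section 9.2 opens by deferring the detail of the effectiveness analysis to the SAP; it does not do so for safety.

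**The concern.** A hypothesis listed as co-primary is one a reader expects to see supported or not supported. Here nothing fixed in advance separates the two outcomes, and the planned output does not show how much the sample can exclude. A short or empty list of adverse device effects (ADEs) could be read as confirming safety when it is also compatible with a risk that matters.

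The design puts one SLActive and one SLA study implant in each patient. That pairing is the natural basis for asking whether events are more frequent with SLActive. Counts by surface show the two totals but not the within-patient contrast or its uncertainty.

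**Working it through.** **1. The plan's own figure.** The only calculated co-primary is bone loss (section 9.4): SDs 0.20 and 0.22 mm, correlation 0, means 0.46 (SLA) and 0.43 (SLActive), margin 0.10 mm, one-sided alpha 0.05, 51 pairs.

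- SD of the difference = √(0.20² + 0.22²) = 0.2973 mm
- Distance from the margin = 0.10 − (0.43 − 0.46) = 0.13 mm
- Noncentrality = 0.13 / (0.2973/√51) = 3.12; noncentral t with 50 df gives 92.4%

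The stated 92.4% reproduces. No corresponding figure exists for safety. Without a null or a criterion, type I error and power are undefined for hypothesis 1.

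**2. What is specified for each question.**

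| | Bone loss (co-primary) | Secondary endpoints | ADEs and deficiencies with SADE potential (co-primary) |
|---|---|---|---|
| Null and margin | yes | no | no |
| Interval | none stated | 95% | none stated |
| Paired analysis | paired sample size; repeated-measures model | repeated-measures model for quantitative endpoints | none stated |
| Output | test of treatment effect | comparison on intervals | listings and tables by surface |

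**3. Precision of a clean or nearly clean table.** The exact (Clopper-Pearson) two-sided 95% upper limit with zero events is 1 − 0.025^(1/n). The values of n come from section 9.4: 60 planned, 51 for power, and 60 × 0.80 = 48 after the stated dropout. The event counts are assumptions.

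| n | Upper limit, 0 events | Interval, 1 event |
|---|---|---|
| 48 | 7.4% | 0.05% to 11.1% |
| 51 | 7.0% | 0.05% to 10.5% |
| 60 | 6.0% | 0.04% to 8.9% |

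Zero events is therefore compatible with a risk of about 1 in 14 (1/0.074) to 1 in 17 (1/0.060).

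**4. How often a clean table would occur.** With 60 patients and true patient-level rate p, P(no event) = (1 − p)^60: about 55% at p = 1%, 30% at 2% and 5% at 5%.

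**5. What the pairing adds.** The uncertainty of the within-patient difference depends on the number of discordant patients, meaning those with an event at one study implant only. Totals by surface do not give that number. For scale only, an exact McNemar test with k discordant patients all in one direction has two-sided p = 2 × 0.5^k: 0.0625 at k = 5 and 0.031 at k = 6. A split of five to none would not reach two-sided 5%.

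**6. Are the data there?** Yes. Section 7.3.12 records adverse events by implant position, 7.3.13 records deficiencies by position where applicable, and 8.2.2 assesses device relationship at study-implant positions.

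**7. Which denominator?** Section 7.2.3 requires lack of primary stability of any implant to be reported as an ADE. Section 3.3 bars such an implant from being a study implant, and 3.7.3 withdraws a patient without a qualifying pair. A table of study implants alone would omit these ADEs by construction; the safety population in 9.3 keeps them.

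**The case against.** Descriptive safety reporting is normal, particularly in a post-market study of CE-marked devices. Section 9.2 itself calls safety a co-primary objective, section 2.1 introduces the hypotheses as expectations, and section 9.4 uses the term primary hypothesis for bone loss. This stands, and it makes the rewording a small step. It does not supply an interval.

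A reader might infer that the control implant is ignored for safety. The documents do not support that. Sections 9.1 and 9.2 require output by treatment group, so SLActive and SLA appear side by side. What is missing is a paired estimate and its precision.

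A reader might also infer that the trial will declare SLActive safe whatever the counts. No section says so, and a bad table could be judged as such. The sponsor reviews every adverse event (8.2), a change in severity, outcome or occurrence can make an expected ADE unexpected (8.2.7), bone level changes above 1.5 mm are flagged (footnote to Table 5), and 11.8 allows early termination for excessive incidence of ADEs. The termination ground carries no number, and the flag opens a discussion about reporting. None is named as a criterion for hypothesis 1.

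Sections 2.2 and 9.2 also link safety and performance to bone level change, which has a 0.1 mm margin. That is hypothesis 2; section 9.2 names ADEs and deficiencies as the answer to hypothesis 1.

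Zero events is an unlikely scenario. Any possible relationship makes an event an ADE (8.1.4), and Table 5 lists pain and swelling as expected. An upper limit of 6% to 7% for such events says little about serious harm. This is fair: the limits illustrate precision and do not predict the result.

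Finally, the separate SAP is not in the supplied text, so a criterion there cannot be excluded. However, 9.2 states the safety method outright and defers only effectiveness.

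**Conclusion.** The point holds in this form: for one of two co-primary hypotheses the plan gives counts by surface, with no interval, no within-patient estimate and no result specified in advance that would count against it. The illustrative size is an exact two-sided 95% upper limit of 7.4% to 6.0% with zero events in 48 to 60 implants. That range assumes one study implant per patient and surface and complete observation. The actual safety set may differ, because it includes patients later withdrawn, some of whom are replaced.

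The documents support no claim that SLActive is unsafe, that a favourable conclusion is guaranteed, or that the surfaces go uncompared. The bone-loss test is unaffected. The change is worth making because it is cheap and bears on a primary claim.

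**What to change.** 1. **Section 2.1 and Synopsis.** Restate hypothesis 1 as a descriptive co-primary objective: to estimate the rate of ADEs and of deficiencies with SADE potential for SLActive, and its difference from SLA. Intervals alone would still leave a hypothesis with no stated way to fail, so the rewording is needed as well.
2. **Section 9.2, paired table.** For patients with both study implants, report per surface the proportion of study implants with at least one ADE or implant-attributable deficiency with SADE potential, with an exact 95% interval. Add the within-patient difference (SLActive minus SLA) with a 95% interval for paired proportions, naming the method in advance (for example a Newcombe or Tango score interval), and show the discordant counts. Keep the planned breakdown by severity.
3. **Section 9.2, full safety population.** Report by surface all ADEs for any BLT implant placed, including lack of primary stability and events in patients withdrawn at Visit 2. Because 8.2.2 asks for device relationship only at study-implant positions, state how ADE status is taken at other positions. List separately the deficiencies of instruments or components that cannot be attributed to one surface.

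The cost is one extra table and a less favourable statement than the present wording. No new data are needed. No acceptable rate is imposed; whether to set one is for the sponsor.

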## 9.3 Analysis populations (Data Sets)

The following analysis populations are planned for this study:

## Safety Analysis Population (SA)

The safety analysis (SA) population consists of all subjects who were enrolled in the study and who received a study device (BLT, Roxolid® implants).

The SA population will be the basis for the safety analysis.

This population includes the ITT population.

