#### 3.7.3 Withdrawal criteria

The Investigator must withdraw any patient from the study in the case of:

- No control and test implants received/ placed at visit 2
- No control and test implant (one of each) available that qualify as study implants (implant is
  assessed as primary stable (as defined in Section 7.2.3) at surgery, the abutment torque is
  at least 15 Ncm at surgery and the implant site fulfills the eligibility criteria, see Section 3.3
  for further details), in 2 different quadrants.

The Investigator may withdraw any patient from the study in the case of:

- Non-compliance with the protocol
- · Failure to attend the follow-up visits
- SAE or AE, which in the opinion of the Investigator prevents the patient's further participation in the study.
- Subject requires surgical treatment during the course of the study in the region of the mouth being evaluated in the study

Any patient may withdraw from the study any time without prejudice and will be offered an alternative treatment related to their dental condition. Patients will be advised of the need for the prescribed follow-up visits for their ongoing care, well-being, and collection of any safety data.

The patient withdrawal will be documented on a Study Termination eCRF page and must include the reason for the patient withdrawal. Withdrawn patients will be replaced in case the recruitment is still ongoing. As soon as recruitment is completed withdrawn patients will not be replaced.

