#### 7.3.13 Device Deficiencies

Device Deficiencies will be recorded for all Straumann products used for the treatment (including prosthetic components and instruments). Device Deficiency collection for each patient will start at Visit 2 (surgery visit) and ends after the last study required treatment.

If a DD leads to an AE (e.g., bleeding, pain, swelling, infection, peri-implantitis) or SAE (e.g., nerve encroachment, sinus perforation, etc.) the respective adverse event eCRF form should as well be completed and the process for adverse events followed (as described in Section 7.3.12 above).

DDs should be documented on the appropriate eCRF form (specifying the article number and Lot.nr of the device concerned and the implant position if applicable) and reported as described in Section 8 of the protocol.

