# Table 5: List of Potential Expected Adverse Events and Adverse Device Effects following dental implant treatment

Dental implant treatments involves implant placement and prosthetic restoration. The table includes AEs and ADEs expected for implant treatment in general and specifically for procedures related to the implant or abutment, without claim to completeness.

	gical complications	Implant	abutment
Gener		······	···•
•	Bruising	X	
•	local inflammation	X	X
•	Local irritation	X	X
•	Swelling	X	
•	Infection at implant site without suppuration (local)	X	X
•	Infection at implant site with suppuration (=peri-implant abscess, local)	Х	X
•	Gingival enlargement (=gingival hyperplasia, gingival hypertrophy, gum overgrowth, hypertrophic gingivitis)	X	
•	Gingival recession (=dehiscence of the gingiva, receding gums)	x	
•	Exfoliation (in connection with the dental implant)	X	
•	Pain	Х	
Hard t	issue related		
•	Low primary stability (at surgery)	X	
•	Implant mobility (tactile horizontal or vertical)	X	
•	Early loss/failure of implant (i.e. before osseointegration)	Х	X
•	Late loss/failure of implant (i.e. after osseointegration)	Х	X
•	Radiolucency	X	
•	Bone necrosis	Х	
•	Bone damage/ fracture	Х	X
•	Delayed healing/osseointegration	Х	
•	Excessive bone resorption/bone loss*	Х	
Syster	nic complications		
•	Asphyxiation	X	X
•	Anaphylaxis	Х	X
•	Slowed recovery after treatment	Х	
•	Implant obstructs patient airway	Х	
•	Allergic reaction/ hypersensitivity to implant material	Х	
•	Allergic reaction/ hypersensitivity to abutment material		X
•	Toxicity reaction	Х	X
•	Systemic infection	Х	X
Other	•	··········	
•	Foreign body sensation	X	
•	Oro-sinus or oro-nasal intrusion/fistula	Х	
•	Permanent paresthesia, dysesthesia	X	Ĭ
•	Chronic pain	X	
•	Nerve damage in the jaw	X	
Mechanical complications		Implant	abutment
•	Implant cannot be placed	X	
•	Loosening of abutment	х	X

Loosening of occlusional screw	Χ	X
Loss/ failure of prosthesis/ reconstruction		X
Loss/failure of an healing cap		X
Fracture/ breakage of abutment		X
Fracture of occlusional screw		X
Fracture of implant	X	

 
Fracture/ chipping of prosthesis / framework
 
	Х	X

 
Implant connection is damaged and non-restorable
 
	Х	

 
Abutment cannot be fixed properly on the implant
 
	X	X

 
Jamming of abutment
 
		X

 
Screw does not fit properly
 
	X	X
Stuck screw	X	X
Bridge does not fit	Х	X
The Crown does not fit		X

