Coping or protective cap does not fit		X
Corrosion of the abutment		X
Irreversible damage to adjacent/opposing teeth or	X	
unfavorably affected adjacent teeth		

 
Loss of cement retention (of prosthesis)
 
		X
Other complications		abutment

 
Esthetic problem/poor aesthetic outcome
 
	X	X
Jaw fracture	X	
Phonetic difficulties	X	X
Aspiration of implant	X	

 
Swallowing of implant
 
	X	
Aspiration of abutment		X
Swallowing of abutment		X

 
Aspiration of component other than implant and abutment.
 
Specify component
 
		

 
Swallowing of component other than implant and abutment.
 
Specify component
 
		

 
Implant burned to mucous membrane (through MRI energy)
 
	Х	
	··· <del>†</del> ······	Χ

\* Based on the 1st European Workshop on Periodontology an average marginal bone loss (MBL) of less than 1.5 mm within the 1st year after the insertion of the prosthesis was specified as criteria for measuring success (43). Based on this information the central radiologist will flag any bone level changes greater than 1.5 mm between implant loading and the 12-months follow-up visit. The study manager will review the flagged values and discuss with the principal Investigator whether the bone level change will be reported as an ADE.

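### The safety population omits patients in whom surgery starts but no implant is placed, and the by-treatment AE summary omits positions where placement failed

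*Combined protocol and SAP*

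**What the plan says.** The second co-primary endpoint (3.4.1) is "Occurrence of adverse device effects and device deficiencies that could have led to a serious adverse device effect". Section 9.2 (Safety and tolerability analysis) addresses it descriptively: an assessment of adverse device effects (ADEs) and "device deficiencies that could have led to a serious adverse device effect will be made, this will include listings and tables by treatment", with no threshold, test or margin.

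The population is fixed in 9.3. The safety "population consists of all subjects who were enrolled in the study and who received a study device (BLT, Roxolid® implants", and "The SA population will be the basis for the safety analysis". The plan's only gloss on *received* is the first mandatory withdrawal criterion in 3.7.3: "No control and test implants received/ placed at visit 2".

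Other sections bear on this:

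- 7.2.1 randomizes after the first implant bed is prepared and before any implant goes in.
- 7.3.12 collects adverse events from screening. Under 7.3.13, "Device Deficiency collection for each patient will start at Visit 2 (surgery visit").
- Table 5 foresees failure at this step and lists "Implant cannot be placed" as a mechanical complication.
- 9.2 restricts the by-treatment AE summary to positions where a BLT implant was placed, or to procedures at those positions.
- 8.2.2 asks for device relationship at the positions of study implants.
- The note in 7.2.3 requires lack of primary stability of any implant to be reported as an ADE.

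**The concern.** Membership of a safety set should not depend on how well the device performed. Here it does at one point. A patient can be incised, drilled and randomized, have a device event that ends the operation, and drop out of the safety denominator because no implant was placed. Section 3.7.3 also has withdrawn patients replaced while recruitment is open, so the headcount would not show the gap.

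The same conditioning on placement recurs one level down. If the SLActive site fails and the SLA site succeeds, the patient is in the set, but an AE at the failed site has no place in the by-treatment summary as 9.2 words it. It also has no clear route to a device-relationship assessment under 8.2.2. An event becomes an ADE through its relationship to the device (8.1.4), so this can affect whether it reaches the co-primary count. At stake is whether the statement that SLActive implants are safe rests on all device events at surgery, attributed to the right surface.

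**Working it through.** **Step 1. Trace each outcome of Visit 2 through the rules.**

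| Outcome at Visit 2 | In safety set (9.3) | AE at that position in by-treatment summary (9.2) | Device relationship assessed (8.2.2) |
|---|---|---|---|
| Implant placed and qualifies as study implant | Yes | Yes | Yes |
| Implant placed and left in, but not primary stable | Yes | Yes | Not as written: it cannot be a study implant (3.3). Yet 7.2.3 calls this an ADE |
| One site fails, an implant is placed elsewhere | Yes | No, for the failed site | Not clearly: the failed site holds no study implant |
| Surgery started, no BLT implant placed | No | No | No |

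Only the last row removes the patient. Rows two and three show the conflict between 8.2.2 and 7.2.3. Device deficiencies are summarized by device type and are not tied to placed positions, so only the safety-set rule can remove them.

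**Step 2. The plan's own figures.** The safety endpoint has no stated rate or target to reproduce. The one powered result, bone level, is unaffected. For reference, the SD of the paired difference is √(0.20² + 0.22²) = 0.2973 mm and the distance to the margin is 0.10 − (0.43 − 0.46) = 0.13 mm. With 51 pairs and one-sided alpha 0.05, the noncentral t gives 92.4%, as stated in 9.4.

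**Step 3. Size.** Inputs:

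- 60 patients (3.5), all assumed to be operated on.
- Two positions per patient, the minimum in 3.7.
- Per-implant placement failure p. The documents give none, so p = 1% to 10% is an assumption.

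Under independence, with N = 60:

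- Expected patients with at least one failed placement: A = N[1 − (1 − p)²]
- Expected patients with both failed, who leave the set: B = Np²
- Chance that at least one patient leaves: C = 1 − (1 − p²)^60

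At the other extreme, a failure at the first position always ends the surgery. The expected number who leave is then D = Np.

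| p | A | B | B/A | C | D |
|---|---|---|---|---|---|
| 1% | 1.2 | 0.006 | 0.5% | 0.6% | 0.6 |
| 2% | 2.4 | 0.024 | 1.0% | 2.4% | 1.2 |
| 5% | 5.9 | 0.15 | 2.6% | 13.9% | 3.0 |
| 10% | 11.4 | 0.6 | 5.3% | 45.3% | 6.0 |

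Under independence, the safety-set rule loses few of the affected patients. Most have one failed site and stay in, so the wording of 9.2 and 8.2.2 matters more often than 9.3.

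**The case against.** The strongest reply is that this is a rare wording gap in a descriptive analysis. One BLT implant of either surface admits a patient, without follow-up or study-implant status. Nothing is lost from the record: AEs and deficiencies are collected in every patient, the sponsor reviews all of them (8.2), serious ones are reported promptly (8.3), and withdrawals are tabulated with reasons. The co-primary ADE tables in 9.2 are also not expressly limited to placed positions, and 7.2.3 asks for treatment complications to be reported as AE or ADE. Most of this stands, and it limits the size. It does not remove the stated rule in 9.3, the restriction in 9.2 or the conflict over device relationship.

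A reader might infer more than the documents support:

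- *Any failed placement, or any mandatory withdrawal, removes the patient.* It does not. Section 3.7.3 withdraws a patient who lacks a qualifying pair, but 9.3 asks for only one implant.
- *The missing events are the most serious ones.* Only "Implant cannot be placed" plainly describes failed placement, and no seriousness is attached to it. Nothing says that "Aspiration of implant" leaves a patient without an implant. Anaphylaxis and bone damage are also marked for the abutment, which is fitted to an implant already in place.
- *The report would show 0/59 (exact 95% upper limit 1 − 0.025^(1/59) = 6.1%) instead of 1/60 (1.7%, 0.04% to 8.9%).* That assumes one such patient, no replacement, and no ADE in anyone else. Section 8.1.4 counts any AE with a possible device relationship, and Table 5 includes pain, swelling and bruising, so a zero count elsewhere is unlikely.

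**Conclusion.** The point holds in a limited form. As written, a patient with surgery started and no BLT implant placed is outside the safety population, and a device event behind that outcome is not in the co-primary safety result. In patients who remain, an AE at a failed position is outside the by-treatment AE summary and not clearly assessed for device relationship, while 7.2.3 already treats lack of primary stability of any implant as an ADE.

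The number affected is likely small. Under the assumed independent failure of 1% to 10% per implant, about 0.006 to 0.6 of 60 patients leave the set and about 1 to 11 have at least one failed placement. The number leaving could approach 0.6 to 6 if a first failure always ended the surgery. If no placement fails, nothing changes. These figures rest on the assumed p, two positions per patient and 60 operated patients. The bone-level result is untouched, and because the safety result has no decision threshold, no formal conclusion turns on this.

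**What to change.** 1. In 9.3, define the safety population as all enrolled subjects in whom the Visit 2 surgery was started (first incision or bed preparation), whether or not an implant was placed. It still contains the ITT population.
2. In 9.2, extend the by-treatment AE summary to positions where placement was attempted. Attribute each event to the surface attempted there or, failing that, the surface randomized to that quadrant. Add an unassigned row for events before allocation.
3. In 8.2.2, extend the device-relationship assessment to the same positions, and reconcile it with the note in 7.2.3 so that one rule decides when an event at a non-study implant is an ADE.
4. Carry the same wording into the SAP.

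For attribution, article and lot number are recorded on the deficiency form only. The AE form carries the implant position (7.3.12), so surface for an AE has to come from that position together with the allocation. In the study quadrants this needs no new visit or assessment. If the surface opened differed from the allocation, the site has to note it. Sample size and power do not change. The cost is a few sentences, a slightly larger denominator and possibly a less favourable event count.
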